7.2 Expected accrual rate, accrual duration, and study duration

Our anticipated accrual rate is 6-8 patients per month. Thus, it should take approximately 3-5 months to accrue the 29 patients needed for the trial. Allowing for 28 days of follow-up to obtain the primary endpoints on the last patient enrolled and 3 months to assemble, analyze and interpret the data the total study duration is projected to be at most 18 months.

7.3 Endpoints

7.3.1 Primary Endpoints

- Transfer to ICU
- 28 day mortality

7.3.2 Secondary Endpoints

- Cumulative incidence of serious adverse events during the study period: transfusion reaction (fever, rash), transfusion related acute lung injury (TRALI), transfusion associated circulatory overload (TACO), transfusion related infection
- Rates and duration of SARS-CoV-2 PCR positivity at days 0, 4, 7, 14 and 21.
- Serum or plasma antibody titer³ to SARS-CoV-2: Day 0, 7, 14, and 28
- Cellular and humoral immune responses at days 0, 7, 14, and 28 days
- Supplemental oxygen free days
- Ventilator free days
- ICU free days
- Sequential organ failure assessment (SOFA) score at days 0, 1, 4, 7, 14, 21, 28
- WHO 8-point scale for clinical improvement at days 0, 1, 4, 7, 14, 21, 28
- Need for vasopressors
- Need for renal replacement therapy
- Need for extracorporeal membrane oxygenation (ECMO)
- Hospital length of stay (LOS)
- ICU LOS
- Grade 3 or 4 adverse events (AEs)

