2. Age \geq 18 years of age
3. No receipt of convalescent plasma

Immunologic Controls:

1. PBMCs with 5-10 million cryopreserved cells per specimen present in the prospective COVID 19 Biorepository
2. Serum or plasma 500 UI each from up to 50 patients present in the COVID-19 Biorepository

Assessment and Data Acquisition:

1. Baseline: Age, sex, comorbidities, date of symptom onset, known COVID-19 contact, type of admission to the floor or ICU, APACHE score (ICU scoring system to classify disease severity and mortality risk), SOFA score (mortality prediction score based on organ function), clinical status, vital signs including temperature, respiratory rate, oxygen saturation, oxygen requirement, neutrophil count, lymphocyte count, CRP, chest x-ray, chest CT, location in hospital.
2. Safety and efficacy: Day 0 (baseline), 1, 2, 3, 4, 7, 14, 21, and 28 and once at day 60.
3. SARS-CoV-2 PCR from OP or NP swabs: Day 0, 4, 7, 14 and at any time when there is clinical suspicion for COVID-19.
4. Outcome measures: increased O₂ requirement (PaO₂/FiO₂ ratio or SpO₂/FIo₂), supplemental oxygen strategy (nasal cannula, high flow nasal cannula, noninvasive ventilation, intubation and invasive mechanical ventilation, rescue ventilation i.e. neuromuscular blocking agents, prone positioning, corticosteroids, ECMO), vasopressors, renal support, ICU LOS, ICU mortality, hospital LOS, hospital mortality, 28 day mortality.
5. Serum or plasma antibody titer² to SARS-CoV-2: Day 0, 7, 14, and 28. Samples from the COVID-19 Biorepository from non-transfused patients will be assayed at two similar timepoints as Immunologic Controls.
6. Blood for immune evaluations of cellular and humoral immunity before CIP infusion (day 0) and 7, 14 and 28 days after CIP infusion. Immune testing may be done at any time if the PI determines there is a need to evaluate acute immune responses (cytokines/chemokines levels). Samples from the Prospective COVID-19 Biorepository from non-transfused patients will be assayed at two similar timepoints as Immunologic Controls.
7. "Clinical controls" will have all relevant datapoints collected via chart review (i.e. biospecimens will not be collected prospectively)

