9. Blood for Immune evaluations of cellular and humoral immunity (4 green tops, 30-40 milliliters).

Day 1-7 (or for duration of hospitalization)

1. Vital signs daily (including supplemental oxygen requirements)
2. COVID-19 symptom screen (fevers, cough, shortness of breath)
3. Assessment of clinical status (8-point ordinal scale)
4. New medical conditions, AE evaluation
5. Physical examination
6. CBC with differential, comprehensive metabolic panel, CRP daily

Days 0, 4 (\pm 1 day), 7 (\pm 2 day), 14 (\pm 3 days), 21 (\pm 3 days), and 28 (\pm 3 days):

1. SARS-CoV-2 PCR from oropharyngeal or nasopharyngeal swabs: Day 0, 4, 7, 14, 21 and at any time when there is clinical suspicion for COVID-19.
2. Serum or plasma antibody titer to SARS-CoV-2: Day 0, 7, 14, and 28
3. Blood for immune evaluations of cellular and humoral immunity before CIP infusion (day 0) and 7, 14, and 28 days after CIP infusion (4 green tops, 30-40 milliliters). Immune testing may be done at any time if the PI determines there is a need to evaluate acute immune responses (cytokines/chemokines levels).

Key issues to consider follow up by phone, alive, at home, in hospital (ICU or not), on supplemental O₂ or not, back to work, fully and partially

- COVID-19 symptom screen (fevers, cough, shortness of breath)
- Assessment of clinical status (8-point ordinal scale)
- New medical conditions, AE evaluation

Day 60 (\pm 7 days):

1. COVID-19 symptom screen (fevers, cough, shortness of breath)

2. Assessment of clinical status (8-point ordinal scale)
3. New medical conditions, AE evaluation

One year (\pm 1 month) - *optional*

- 1. Serum or plasma antibody titer to SARS-CoV-2**
- 2. Blood for immune evaluations of cellular and humoral immunity**
- 3. CBC with differential, Comprehensive metabolic panel, PT/INR, PTT, Quantitative immunoglobulins**
- 4. Interval medical history**
- 5. Subject questionnaires regarding health status**

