8.2 Virologic measures

1. Rates, levels and duration of SARS-CoV-2 RNA in OP or NP swabs and/or subgenomic - messengerRNA (sg-mRNA) from Viral Transport Media (VTM) by RT-PCR at days 0, 4, 7, 14, and 21. Other specimen types may be tested as available (e.g. BAL fluid, tracheal secretions, sputum, etc.) or when RT-PCR assays are validated for additional sources (i.e., stool, blood). VTM will be obtained from the original OP or NP swab collection devices as detailed above. Trial patient samples will be compared to control non-transfused hospitalized patient samples stored in the clinical labs.
2. Serologic positivity and neutralization antibody titers for anti-SARS-CoV-2 at days designated time points at 0, 7, 14, and 28.

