9.0 STATISTICAL CONSIDERATIONS

9.1 Power calculation

Twenty-nine evaluable patients will have 80% power to declare a significant decrease in ICU admissions from a historical control of 50% of hospitalized patients to 25% with a two-sided type I error of 0.05 (reject ICU admission rate=50% if only 8 or less patients are admitted to ICU among 29 evaluable patients).

Data analysis: For categorical clinical endpoints, frequency with percentage will be summarized. For the quantitative clinical variables and immune response variables measured in this objective, we will produce summary statistics (including means, medians, and standard deviations) for data at pre- and post-CIP infusions. Subsequent analyses will compare the serologic and neutralization antibody titers for anti-SARS-COV-2 antibodies and immune response variables (after a suitable data transformation to improve normal distribution, if necessary) pre- and post-treatment using a paired t-test (or Wilcoxon sign ranked test if the data are not approximately normally distributed). The level of each measured immune biomarker measured at the follow-up time points will be plotted to visually show the change of immune responses over time. To explore whether immune responses at pre- or peak improvement at post-CIP infusions associate with clinical endpoints (such as ICU admission, intubation), logistic regression for binary endpoints and Cox regression for time to event endpoints will be used to analyze each measured immune biomarker respectively. These effects will be compared to biospecimen from non-transfused immunologic controls. Analyses will adjust for other covariates such as age and co-morbidities. No

multiplicity adjustment is planned due to the nature of being exploratory. A two-sided p-value of < 0.05 will be considered significant.

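### Duration of PCR positivity is interval-censored between swabs and right-censored at the last one, but the plan names no censored-data method for it

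*Combined protocol and SAP*

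**What the plan says.** Section 7.3.2 lists "Rates and duration of SARS-CoV-2 PCR positivity at days 0, 4, 7, 14 and 21" among the secondary endpoints, and section 8.2 has the matching virologic measure, "Rates, levels and duration of SARS-CoV-2 RNA in OP or NP swabs".

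The visit plan in section 5.2.7 schedules "SARS-CoV-2 PCR from oropharyngeal or nasopharyngeal swabs: Day 0, 4, 7, 14, 21 and at any time when there is clinical suspicion for COVID-19". It allows windows of ±1, ±2, ±3 and ±3 days at days 4, 7, 14 and 21. Table I shows the same days, and no PCR is scheduled after day 21. The assessment list in the Summary (section 1.0) differs, with "SARS-CoV-2 PCR from OP or NP swabs: Day 0, 4, 7, 14 and at any time when there is clinical suspicion for COVID-19" and no day 21, although the Summary's own list of secondary endpoints includes that day.

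The only general analysis text is in section 9.1. Categorical clinical endpoints get frequencies and percentages. For quantitative clinical and immune variables, "we will produce summary statistics (including means, medians, and standard deviations". Cox regression is named, but only to relate immune biomarkers to clinical endpoints. PCR duration is not mentioned there. The documents do not define when positivity ends. They give no rule for a patient still positive at the last swab, for a missed swab, or for death before clearance.

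**The concern.** A duration read from intermittent swabs is an interval, and for patients still positive at the last swab it is open-ended. A mean or median forces one number on each patient. The analyst must choose the last positive day, the first negative day or something between, and then decide whether patients still positive at day 21 count as 21 or are left out. With no rule in the plan, the choice can be made after the data are seen, and it shifts the answer. Unscheduled swabs taken on suspicion narrow the interval for some patients and not others, so the error need not be the same across patients.

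At stake is one descriptive secondary endpoint in the plasma recipients. It bears on the trial's rationale, since section 3.2 cites reduced viral load as early evidence for the treatment.

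**Working it through.** The plan states no figure for PCR duration, so there is none to reproduce.

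**Swab gaps.** Nominal gaps are 4, 3, 7 and 7 days. With the windows the largest gaps are 5 − 0 = 5, 9 − 3 = 6, 17 − 5 = 12 and 24 − 11 = 13 days. The last swab can fall on days 18 to 24.

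**Model (assumed).** The documents give no clearance distribution. Take clearance time T after day 0 as Weibull, S(t) = exp[−(t/λ)^k], with λ = median/(ln 2)^(1/k). All patients are positive at day 0 and swabbed on the nominal days, with no return to positive after a negative. Patients still positive at day 21 are scored 21.

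**Worked case: k = 2, true median 14.** λ = 14/(0.693)^0.5 = 16.82, and the true mean is λΓ(1.5) = 14.9. S(4), S(7), S(14), S(21) = 0.945, 0.841, 0.500, 0.210. The four gaps therefore hold 0.055, 0.104, 0.341 and 0.290 of patients, and 0.210 are still positive.

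- Last positive: 0 + 4(0.104) + 7(0.341) + 14(0.290) + 21(0.210) = 11.3, error −3.6.
- First negative: 4(0.055) + 7(0.104) + 14(0.341) + 21(0.290) + 21(0.210) = 16.2, error +1.3.
- Midpoint: (11.27 + 16.22)/2 = 13.75, error −1.2.

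**Error of the mean, in days, over the range:**

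| k | True median | Positive at day 21 | True mean | Last positive | First negative | Midpoint |
|---|---|---|---|---|---|---|
| 1.5 | 7 | 3% | 8.1 | −2.4 | +2.6 | +0.1 |
| 1.5 | 10 | 12% | 11.5 | −3.1 | +1.9 | −0.6 |
| 1.5 | 14 | 28% | 16.1 | −4.7 | −0.5 | −2.6 |
| 1.5 | 18 | 42% | 20.7 | −7.2 | −3.7 | −5.5 |
| 2 | 7 | <1% | 7.5 | −2.3 | +2.9 | +0.3 |
| 2 | 10 | 5% | 10.6 | −2.8 | +2.8 | 0.0 |
| 2 | 14 | 21% | 14.9 | −3.6 | +1.3 | −1.2 |
| 2 | 18 | 39% | 19.2 | −5.3 | −1.4 | −3.3 |

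Of the 16 last-positive and first-negative errors, 12 are between 1.9 and 5.3 days in size. A longer tail is worse: k = 1, median 14 (35% still positive) gives −8.8, −5.3 and about −7. Dropping patients still positive, instead of scoring them 21, gives −6.2, +0.1 and −3.1 for k = 2, median 14.

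**Medians at n = 29** (600 simulated trials per scenario; k = 1 and 2; true medians 7, 10, 14, 18). Average error was −1.5 to −3.7 days for last positive, +1.6 to +4.0 for first negative and −1.0 to +1.1 for midpoint. An interval-censored Weibull fit gave −0.01 to +0.6 in seven of eight scenarios and +1.2 in the eighth (median 18, k = 1). That comparison favours the fit, because the data were Weibull.

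**The case against.** The strongest reply is that the plan does not prescribe a poor method; it prescribes none. Section 9.1 attaches its means and medians to data before and after infusion, and a duration has no pre-infusion value. Percentages already cover the rates half of the endpoint. This stands: a reader might infer that the plan commits to a biased estimator, but the documents show only a default that would apply by inference.

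A reader might also infer that the estimate will be wrong by days. That depends on an assumed distribution and an unstated scoring rule. First-negative scoring is within half a day in one row of the table, and midpoint means are within 0.3 day in three of the four rows with few patients still positive. Midpoints do not deal with right-censoring, however. Their small average error in the median is also partly cancellation. With 29 patients on nominal days the midpoint median can only be 2, 5.5, 10.5, 17.5 or 21, so a true median of 14 is missed by at least 3.5 days in every trial.

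A 7-day difference between last-positive and first-negative medians would be poor evidence, since it restates the swab gap, and a true median of 14 sits on a swab day. Nor can the error be called as large as a treatment effect: the documents give no effect size for this endpoint, and the point concerns the recipients' own estimate. Finally, a Turnbull median may be placed only within a gap, and a Weibull median leans on the model. Both limits are real.

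**Conclusion.** The concern holds as a gap in the analysis text. Duration of PCR positivity is interval-censored by design and right-censored at the last swab, and no method for that is named. If simple summaries are used, they can be off by several days. The size is about 2 to 5 days in most scenarios for last-positive or first-negative scoring, in either direction. For midpoint means it is roughly 1 to 5 days too short (1.2 to 5.5 in the table) once about 20% to 40% remain positive at day 21. These figures rest on Weibull clearance with shapes 1.5 to 2 and true medians of 7 to 18 days, none of which comes from the documents.

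The percentage positive at each scheduled day, among patients swabbed, is not affected. Nor are ICU transfer, 28-day mortality or the decision rule. For one secondary endpoint in a 29-patient single-arm study this is a minor priority.

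**What to change.** In the data-analysis text of section 9.1, replace means and medians for this endpoint with an interval-censored analysis on actual swab dates:

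- Lower bound: last positive swab. Upper bound: first negative swab. State a rule for a negative followed by a positive.
- Still positive at the last swab: right-censored there. Death before clearance: counted as not cleared by day 21.
- Unscheduled swabs serve only to narrow a patient's interval.
- Main summary: proportion cleared by days 7, 14 and 21, with 95% confidence intervals.
- Supporting summary: the Turnbull median interval, or a Weibull median labelled as model-based, with a 95% confidence interval.

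Reconcile the assessment list in the Summary, which omits day 21, with sections 5.2.7, 7.3.2 and 8.2 and Table I, because the last swab day sets where right-censoring falls.

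The cost is one paragraph and standard software, with no new visits, samples or patients. The reported interval will be wider, and the median may be located only within a swab gap.

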5.2.7 Enrollment, Screen Failures, and Study Completion

Patients are considered enrolled from time consented to participate until designated as a screen failure or have either been discontinued from the study or completed it. A screen failure is a patient who signed informed consent, but then was determined to be ineligible or withdraws from the study. Subjects are considered to have completed the study when they are followed through day 60 or have had an adverse event or death occurred prior to day 60.

Day -1 to 0 Baseline:

- A. Subject informed consent (obtained before performing study related activities)
- B. Baseline Evaluation at screening.
 1. Demographics (Age, sex ethnicity, race)
 2. Medical history (timing of exposure to COVID-19 source patient, acute and chronic medical condition, medications, allergies.) Any medical condition arising after consent should be recorded as AE.
 3. COVID-19 symptom screen (fevers, cough, shortness of breath, diarrhea, anosmia), onset of symptoms, source of contagion
 4. Vital signs

5. COVID-19 testing (RT-PCR) from nasopharyngeal, throat, tracheal aspirate or bronchoalveolar lavage and stool (optional) samples
6. Blood typing, CBC with differential, comprehensive metabolic panel
7. Serological testing: anti-SARS CoV-2 titers
8. Immune testing samples
9. Urine or serum pregnancy test for females of childbearing potential. Results from laboratory tests obtained up to 7 days before enrollment may be used for the pregnancy test.
10. Determination of eligibility as per inclusion/exclusion criteria, age, consent, positive for COVID-19, respiratory symptoms within 72 hours of admission

DAY 0 Baseline and Infusion:

1. Study Plasma Administration: 1-2 units of plasma will be transfused over 1-2 days. Time at start and end of infusion will be recorded and vital signs will be measured immediately prior to infusion, 10-20 minutes after start of infusion, at completion of infusion and 30-60 minutes after the end of the infusion
2. COVID-19 symptom screen (fevers, cough, shortness of breath)
3. Assessment of clinical status (8-point ordinal scale)
4. New medical conditions, concomitant medication, AE evaluation
5. Physical examination
6. COVID-19 testing (RT-PCR) from nasopharyngeal, throat or stool (optional) samples
7. Blood typing, CBC with differential, comprehensive metabolic panel, C-reactive protein
8. Serological testing: anti-SARS CoV-2 titers

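### Hospital and ICU length of stay are efficacy endpoints with no rule for patients who die, so the planned summaries do not give an interpretable comparison with the chart-review controls

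*Combined protocol and SAP*

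**What the plan says.** Section 7.3.2 names "Hospital length of stay (LOS" and ICU LOS among the secondary endpoints, and section 8.1 (Clinical Efficacy) lists both again. Neither place gives a start, an end, a horizon, or a value for a patient who dies or never enters the ICU. Oxygen-, ventilator- and ICU-free days appear in the same lists, also without a window or a death rule.

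For quantitative clinical variables, the data analysis paragraph of section 9.1 states "we will produce summary statistics (including means, medians, and standard deviations". The one time-to-event method has a different purpose: "logistic regression for binary endpoints and Cox regression for time to event endpoints will be used to analyze each measured immune biomarker respectively".

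Death is a separate endpoint: "28 day mortality" is primary in section 7.3.1, and section 8.1 adds day 60. Section 5.2.7 treats subjects as having completed the study if they "have had an adverse event or death occurred prior to day 60", so a stay cut short by death is not marked as incomplete.

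The Summary and section 2.3 say that recipients will be compared with controls drawn from chart review. Section 7.1 makes these 29 patients matched on sex and age.

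**The concern.** LOS is cut short by two opposite outcomes, recovery and death. A plain mean or median treats them alike unless a rule separates them, and the plan has none. A difference in LOS between recipients and controls could then reflect when patients died, not how fast they recovered.

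The groups may well differ in early deaths. Controls qualify on their status at admission (section 4.3). Recipients enrol within 72 hours of admission (section 4.1) and leave the trial if, before infusion, they come to need ventilation or oxygen above the entry limit (section 5.2.6). Early deterioration can therefore enter the control data and be missing from the treated data.

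ICU LOS has a second problem. If it is averaged only over patients who entered the ICU, it conditions on ICU transfer, which is itself a primary endpoint. A treatment that changes who is transferred changes the group being averaged.

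**Working it through.** **The plan's own figure.** The documents give no figure for LOS. Their one sample-size statement concerns ICU transfer: "Twenty-nine evaluable patients will have 80% power to declare a significant decrease in ICU admissions from a historical control of 50" per cent "to 25% with a two-sided type I error of 0.05". By the normal approximation, n = [(1.960 × √(0.5 × 0.5) + 0.842 × √(0.25 × 0.75)) / 0.25]² = 28.92, which rounds up to 29, with power 80.1%. Only the group size of 29 and the two transfer rates are used below.

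**Hospital LOS.** The documents give no stays, so these are assumptions: 22 patients stay 7 days and 7 stay 20 days.

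- No deaths: (22 × 7 + 7 × 20) / 29 = 294 / 29 = 10.1 days.
- Now let 4 of the 7 long-stay patients die on day D, with the stay ending at death: mean = (154 + 60 + 4D) / 29.

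| Day of death D | Sum of days | Mean LOS | Change |
|---|---|---|---|
| 3 | 226 | 7.8 | −2.3 |
| 14 | 270 | 9.3 | −0.8 |
| 20 | 294 | 10.1 | 0 |
| 25 | 314 | 10.8 | +0.7 |

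- Deaths dropped: (154 + 60) / 25 = 8.6 days, whatever the day of death.
- Median: the 15th of 29 ordered values is 7 days in every row, because 22 patients share that value.

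**Sensitivity to the assumptions.** Take 6 deaths among 29, survivor stays of 8 to 14 days and deaths on days 3 to 7. The mean falls by 0.2 to 2.3 days if the stay ends at death. It rises by 2.9 to 4.1 days if each death is set to 28 days. For example, with survivors at 10 days and deaths on day 5, the two rules give (230 + 30) / 29 = 9.0 and (230 + 168) / 29 = 13.7, against 10.0 with no deaths.

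The stable median above comes from the tied values. In a simulation with skewed stays (survivor median 8 days, 6 deaths between days 2 and 8), the median goes from 8.1 to 7.0 days if stays end at death, and to 9.9 if deaths are set to 28 days.

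**ICU LOS.** The planned rates imply about 14 transfers in 29 at 50% (14.5) and 7 at 25% (7.25). Assume that the 7 prevented ICU stays would have lasted 5 days and the other 7 last 14 days.

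- ICU patients only: before, (7 × 5 + 7 × 14) / 14 = 133 / 14 = 9.5 days; after, 98 / 7 = 14.0 days. Success on ICU transfer appears as a longer ICU stay.
- All 29, with 0 for no ICU stay: before, 133 / 29 = 4.6 days; after, 98 / 29 = 3.4 days. The direction reverses.

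**The case against.** A reader might infer that the plan scores an early death as a short, favourable stay and so leans towards plasma. The documents do not support that. They state no scoring rule at all, and the summary sentence in section 9.1 is framed around values before and after infusion, which fits LOS poorly. Excluding deaths is equally open. Even if stays end at death, the direction depends on timing: in the illustration, deaths on day 20 change nothing and deaths on day 25 lengthen the mean. The median, which the plan also reports, does not move there. Nor does ICU LOS necessarily look like harm when transfers fall; that needs non-ICU patients to be left out.

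The stakes are also limited. The two LOS items are 13th and 14th of 15 secondary endpoints, no LOS test is specified, and the rejection rule ("reject ICU admission rate=50% if only 8 or less patients are admitted to ICU among 29 evaluable patients") does not involve them. Mortality is a primary endpoint, and the Summary lists hospital and ICU mortality among the outcome measures, so excess deaths would be visible beside a shorter stay.

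All of this stands, and it limits both direction and severity. It does not supply the missing rule. A mortality figure in another row does not tell the reader how to correct a mean LOS, and the choice among the open rules can reverse the sign of the difference.

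**Conclusion.** The point holds as a gap in the analysis of secondary efficacy endpoints. With no rule for death, LOS cannot be interpreted as a comparison with chart-review controls, and ICU LOS restricted to ICU patients would not be a fair comparison. No particular direction of bias can be claimed.

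In the 29-patient illustration, four deaths move the mean by anything from −2.3 to +0.7 days depending on when they occur. These figures rest on assumed stays and show possible size and direction only. Severity is modest. The primary analysis of ICU transfer is unaffected, but the change should be made because the remedy is better than the planned summary and costs little.

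**What to change.** In sections 7.3.2, 8.1 and 9.1:

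- **Hospital stay.** Compare time to discharge alive through day 28, as cumulative incidence with death as a competing event. A patient who dies in hospital never counts as discharged.
- **Time zero.** Define it the same way for both groups. Day 0 is now the infusion (section 5.2.7), which controls do not have. Hospital admission is one option. Another is a matched day after admission that respects the 72-hour enrolment window, with the control still alive and on the floor that day; this better handles the wait for infusion.
- **Free days.** Count ventilator- and ICU-free days over the same 28 days in all patients, with death by day 28 scored 0. Use ICU-free days in place of ICU LOS for the comparison.
- **Oxygen-free days.** Apply the same rule, but limit it to in-hospital oxygen or state an assumption for controls after discharge. Section 5.2.7 plans telephone follow-up that covers oxygen use for study subjects; controls have chart data only.
- **Raw LOS.** Report it descriptively, separately for survivors and non-survivors.

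The cost is protocol and SAP wording, plus abstraction of discharge and death dates for controls. The Summary lists LOS and mortality as outcomes but does not list those dates. LOS becomes descriptive only. Treatment, visits and sample size do not change.
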